1.0 Specific Aims

Post-operative nausea and vomiting (PONV) is a common problem that significantly impacts patient comfort and satisfaction and can delay discharge. The breast surgery population is especially at risk for PONV, given that 2 of the leading risk factors for PONV, female gender and use of peri-operative narcotics, are nearly universal. While the use of prophylactic anti-emetics significantly reduces the incidence of PONV, it still remains a significant problem, especially among high risk patients (i.e., those with a history of PONV or motion sickness). Stimulation of the acupoint Pericardium 6 (P6) has been demonstrated to be effective at both preventing and treating nausea and vomiting in multiple settings and has specifically been demonstrated to be as effective as pharmacological anti-emetics in PONV.[1] However, the role of P6 as an adjunct to multi-agent prophylaxis is less clear. P6 stimulation can be accomplished through needle insertion, acupressure, or electrical stimulation. Recently, two randomized trials in Europe and Asia have reported positive results in PONV prevention using intra-operative electrical stimulation of P6 with a neuromuscular blockade monitor (NMBM).[2, 3] The advantage to this method is that it employs a standard anesthesia tool, and, beyond anesthesiologist training on P6 point location, requires no additional resources for implementation. However, both of these trials compared NMBM to no prophylaxis rather than as an adjunct to pharmacological prophylaxis. We recently presented a small case series in which we employed intraoperative NMBM stimulation of P6 along with pharmacological prophylaxis in patients with a history of PONV (despite previous pharmacological intervention) and found that none of these patients developed PONV with the combined treatment modalities.[4]

The proposed two-arm, randomized, double-blind (patient and assessor), controlled study will determine the initial efficacy and feasibility of anesthesiologist-provided intraoperative NMBM electrical stimulation of P6 combined with prophylactic anti-emetics versus pharmacological prophylaxis alone in women at high-risk for PONV undergoing breast surgery. This study will provide preliminary evidence of efficacy to inform the design of a larger multi-institutional trial. We will also explore predictors of response to P6 stimulation including genetic polymorphisms and expectancy. The aims of the proposed study are to:

PRIMARY AIM:

1. Examine the efficacy of electrical stimulation of P6 combined with prophylactic anti-emetics versus pharmacological prophylaxis alone in preventing the incidence of PONV following breast surgery in patients at high-risk for PONV.

SECONDARY AIMS:

1. Determine the study feasibility and effects on severity of PONV of anesthesiologist-provided intraoperative NMBM electrical stimulation of P6 combined with prophylactic anti-emetics in women at high-risk for PONV undergoing breast surgery.
2. Examine the effects of intra-operative NMBM stimulation of P6 on need for rescue anti-emetics compared to the control group.

3. Examine group differences in post-operative patient satisfaction with PONV management.
4. Explore if intra-operative NMBM stimulation of P6 results in decreased PACU length-of-stay and decreased rate of unplanned hospital admission
5. Explore the associations between genetic polymorphisms in COMT, 5HT3, OPRM1, and DRD2 and response to P6 stimulation.
6. Explore the associations between expectancy and response to P6 stimulation.

2.0 Background and Significance

PONV is a common occurrence following breast surgery, with incidence reported as 30-70% in the contemporary era.[5, 6] The high rate of PONV in this population is unsurprising given that the most well-validated risk score for PONV, the Apfel score, includes 4 variables (female gender, anticipated post-operative use of narcotics, history of PONV or motion sickness, and non-smoking status) two of which are nearly universal in this population.[7] Though not examined in the original risk stratification systems, there is also an association between chemotherapy-induced nausea and vomiting (CINV) and PONV[8], which becomes relevant in an era of increasing use of neoadjuvant chemotherapy. By delaying discharge from the PACU and leading to unanticipated admission following ambulatory surgery,[9] PONV is estimated to add hundreds of millions of dollars annually to the cost of post-op care in the US.[10] In addition, prevention of PONV is a major determinant of patient satisfaction.[11]

Multi-modal anti-emetic prophylaxis employing corticosteroids, serotonin antagonists, histamine antagonists and/or dopamine antagonists significantly reduces the incidence of PONV.[12] However, PONV remains a major problem for some high-risk patients, defined as having three or more of Apfel score variables who have a predicted risk of PONV of over 60% without prophylaxis.

Evidence for P6 in PONV

One promising non-pharmacological approach to the prevention of PONV is stimulation of the acupoint Pericardium 6 (P6 or alternatively called PC6). Based on large meta-analyses and systematic reviews, P6 stimulation is recommended by consensus guidelines of the Society for Ambulatory Anesthesia as a non-pharmacological approach for the prevention of PONV, given that its efficacy has been found to be similar to prophylactic antiemetics including ondansetron, metoclopramide, and prochlorperazine.[13]

Acupuncture has been used as a treatment for various GI disturbances in China for thousands of years. The acupoint P6, located over the median nerve, on the palmar aspect of the forearm, is the most frequently used and well-studied point for the prevention and treatment of nausea and vomiting. The use of P6 in preventing PONV was first reported in the west by Dundee in 1986 following a trip to China.[14] In 1996, the first systematic review of acupuncture for nausea and vomiting was performed, which included 33 trials with 27 favoring P6.[1] Based on this data, in 1998 the National Institutes of Health Consensus Development Panel on acupuncture concluded that there was promising data supporting the use of acupuncture in PONV and CINV.[15] A 2009 Cochrane review specifically on P6 stimulation for the prevention of PONV examined 26 trials and over 3300 patients.[16] When compared to sham, P6 stimulation was found to be more effective in preventing nausea (relative risk [RR] 0.72; 95% CI 0.56–0.91). In the nine trials which compared P6 to various antiemetics, there was no reliable difference found between antiemetics and P6 stimulation for prevention of either nausea (RR 0.82; 95% CI 0.60–1.13) or vomiting (RR 1.01; 95% CI 0.77–1.31). While in some cases, P6 stimulation could be considered as an alternative to pharmacological anti-emetics given non-inferior efficacy and superior safety profile, the effects of anti-emetics of different classes are additive and thus the standard of care for patients at moderate or high risk of PONV is multi-agent prophylaxis.[13] Lee's 2009 review included only one study where P6 stimulation was combined with pharmacological prophylaxis and the results of this trial were unclear.[16] A Pubmed search for trials published since 2008 of P6 stimulation for PONV found 5 trials which have evaluated P6 as an adjunct to pharmacological anti-emetics, with four of the five trials showing significant benefit to adding P6 stimulation to prophylactic anti-emetics. [17-21]

Despite strong evidence from almost 30 years of trials of P6 stimulation in the prevention of PONV, there does not seem to be significant penetration of this modality into clinical practice. One factor limiting adoption is likely the burden of introducing new personnel or equipment into the peri-operative and operative

spaces. There are a number of different methods employed to stimulate P6 including traditional needle-penetrating acupuncture, electro acupuncture in which an electrical stimulating device is connected to the needle, transcutaneous electrical stimulation, or acupressure, either manual or with a commercially available band. In Lee's 2009 review, there was no significant difference in the effectiveness of the various modalities though there were no head-to-head comparisons. However, while these methods may not vary in effectiveness, they do vary widely in ease and cost of implementation. Recently, there have been a series of studies which employed peripheral nerve stimulators used to monitor neuromuscular blockade in the operating room to stimulate P6 intra-operatively to prevent PONV. [2, 3, 22, 23] Monitoring of neuromuscular blockade by electrical stimulation of a peripheral nerve is standard in modern anesthesia when a neuromuscular blocking agent is used. The degree of muscle activity elicited by a peripheral nerve stimulator, usually placed on the ulnar or facial nerve, indicates the depth of neuromuscular blockade, allowing the anesthesiologist to appropriately adjust dosing and thus decrease the incidence of side effects. The advantage to using a NMBM is that this is standard equipment used by anesthesiologists and is therefore easily generalizable as it does not require bringing in additional equipment or personnel.[24] Four recent studies using NMBM at P6 in patients undergoing laparoscopy have demonstrated that this may be an effective mode of stimulating P6 to prevent PONV, including 2 RCTS of over 200 patients each. [2, 3, 22, 23] However, none of these studies examined NMBM stimulation of P6 as an adjunct to pharmacological anti-emetics.

Mechanism of P6 in nausea and vomiting

The Chinese name for P6, Neiguan, means inner gate. The traditional uses for this point include calming the spirit and harmonizing the stomach. The mechanism by which P6 stimulation exerts anti-nausea effects remains unclear. Controlled animal and human studies have demonstrated changes in gastric motility and lower esophageal sphincter relaxation with P6 stimulation.[25-27] This appears to be vagally mediated given abolishment of the effects by vagotomy in a rabbit model. [28] In healthy human volunteers, P6 stimulation has been demonstrated to increase vagal modulation as measured by heart-rate variability. This is postulated to be via a somatoautonomic reflex involving a somatic afferent pathway and vagal efferent path. Another postulated mechanism of action is via the neurotransmitters serotonin and dopamine, which are also the targets of the most effective pharmacological anti-emetics. This hypothesis is largely extrapolated from the acupuncture analgesia literature where acupuncture's effects on levels of endogenous opioids and dopaminergic and serotonergic signaling have been well-documented.[29] Recently, in a trial of P6 stimulation for CINV, serum levels of dopamine and serotonin decreased in the treatment group but not the control group.[30]

Genetics of PONV

The risk of PONV is related to both anesthesia-specific factors such as the use of inhalational anesthetics and narcotics, as well as patient-specific factors such as female gender and smoking status. Patients with a history of either PONV or motion sickness are nearly twice as likely to experience PONV, and there is also some suggestion that tendency to PONV or motion sickness may be familial, raising the potential of a genetic predisposition.[31] Over the past 5 years, there have been a number of studies conducted to identify genetic polymorphisms associated with increased risk of PONV or CINV as well as pharmacogenomic studies focused on polymorphic variations of either the targets for specific antiemetics or metabolic enzymes to probe heterogeneity of response (reviewed in Janicki et al 2014). Reflecting the multitude of pathways involved in the pathogenesis of nausea and vomiting, genetic variants of the receptor genes for serotonin, dopamine, and opioids among others have all been found to be associated with individual susceptibility to nausea and vomiting and/or response to anti-emetics.[31] Interestingly, single-nucleotide polymorphisms (SNPs) in the O-methyltransferase gene, COMT, have recently been found to be associated with response to acupuncture in aromatase-inhibitor induced arthralgias.[32] COMT is an enzyme that regulates dopamine catabolism and in animal models acupuncture has been shown to regulate dopamine release and transmission.[33, 34] COMT polymorphisms have also been demonstrated to be associated with differential risk of PONV and post-operative pain.[35]

In order to better understand predictors of response to acupuncture for nausea and vomiting, we will examine polymorphisms of candidate genes which have been associated with risk of nausea and vomiting and with overlapping biological plausibility of acupuncture's mechanism of action. Specifically, we propose to examine SNPs in COMT, the 5-HT₃ receptor, the mu-opioid receptor gene (OPRM1), and the Dopamine D₂

receptor (DRD2). These findings could help elucidate the heterogeneity of acupuncture treatment response and potentially allow for personalized therapeutic approaches in the future.

Expectancy

Years of psychological research have found that expectancy is an important factor viewed as a “non-specific” effect of behavioral and pharmacological therapies. In particular, response/outcome expectancy may produce important clinical changes [36]. In a systematic review, Crow et al. [37] showed that when clinicians stated positive outcome expectations as opposed to uncertain expectations, most studies found improvements in patient self-reports of anxiety, pain, and distress. A few studies have explored the association between expectancy and clinical outcomes in the context of acupuncture [38, 39]. While these studies provided preliminary evidence that greater expectancy may produce better clinical response, none used a validated instrument to measure expectancy. A recent trial using a validated acupuncture expectancy questionnaire found that expectancy of benefit had a differential effect on outcomes based on whether patients were receiving real versus sham acupuncture [32]. In a trial of acupuncture to treat aromatase-inhibitor arthralgia in breast cancer survivors, Mao et al. reported that for patients in the sham acupuncture group there was a positive association between baseline expectancy and pain reduction. In contrast, there was no association between baseline expectancy and pain reduction in the real acupuncture group. Investigating expectancy as part of the complex mind-body interactions of acustimulation will likely yield important knowledge that is both scientifically sound and clinically meaningful to patients at risk for PONV.

3.0 Research Design and Methods

We will conduct a two-arm, randomized, double-blind, controlled trial comparing pharmacological prophylaxis alone versus intraoperative NMBM stimulation of the acupoint P6 + pharmacological prophylaxis to prevent PONV in women undergoing breast surgery. P6 stimulation with an NMBM monitor will be performed by the attending anesthesiologist and will commence after induction and be removed at the end of surgery. Patients and assessors will be blinded to group assignment. The primary endpoint is the incidence of PONV. Secondary endpoints include feasibility, severity of PONV, rescue anti-emetic use, patient satisfaction, time in PACU and hospital admission rate. We will also explore predictors of response to P6 stimulation including genetic polymorphisms and expectancy. The data provided by this preliminary study will be used to design a larger multi-institutional trial.

3.1 Patient Eligibility

Inclusion criteria:

1. Adults at least 18 years of age
2. Female gender
3. History of patient reported PONV, CINV or motion sickness
4. Patients scheduled for Breast Surgery
5. Sign an informed consent indicating they are aware of the investigational nature of this study.

Exclusion criteria:

1. Patients scheduled for paravertebral block
2. Upper extremity deformity contralateral to the site of disease that could interfere with accurate point location or alter the energy pathway as defined by traditional acupuncture theory
3. Local skin infections at or near the acustimulation site
4. Pre-existing nausea and vomiting, defined as nausea or vomiting requiring pharmacological treatment greater than 3 times in the week preceding screening
5. History of CVA or other central nervous system disorder resulting in residual weakness or paresis of

- extremity contralateral to the site of disease
- 6. Grade III or IV upper extremity peripheral neuropathy
- 7. Cardiac pacemakers. Patients involved in this protocol will receive electrical stimulation. For safety reasons, electrical stimulation should be avoided in patients with pacemakers
- 8. Metal implants to the treatment extremity. For safety reasons, use of electrical stimulation should be avoided
- 9. Current acknowledged use of any illicit drugs, medical marijuana (including Marinol), or evidence of alcohol abuse as defined by The American Psychiatric Association criteria [41]. This includes patients who are currently in the recovery process.
- 10. Pregnancy as this would alter anesthesia plan
- 11. Bowel obstruction
- 12. Surgery that would not allow access to at least one P6 site.

3.2 Participants

Over 1000 patients undergo ambulatory breast surgery each year at MD Anderson Cancer Center. Approximately 30% of these patients receive a paravertebral block and would therefore be ineligible for this study as these patients would be expected to have a lower incidence of PONV and the block could potentially interfere with acupoint stimulation mechanism of action. On initial chart review, it appears that approximately 50% of patients would meet our eligibility criteria of being high-risk based on a history of either PONV, CINV or motion sickness, which leaves approximately 350 eligible patients per year. All eligible participants will be approached. In previous acupuncture studies of other indications, our acceptance rate has been 70-80% and attrition rate 25%. However, given that this study employs a non-needle intervention and does not require a series of treatments over a protracted period of time as in our other studies, we would expect a higher acceptance rate and no attrition, though we still may have a few drop-outs between randomization and intervention. Thus, with conservative estimates of 70% acceptance and including a 5% drop-out rate, we would expect to be able to accrue the planned 176 patients in 10 months.

3.3 Treatment Plan

The experimental group will receive anesthesiologist-provided intraoperative NMBM electrical stimulation of P6 combined with prophylactic anti-emetics, while the control group will only receive prophylactic anti-emetics.

Recruitment and registration

This study will be conducted at the University of Texas MD Anderson Cancer Center (MDACC). Patients will be identified from the breast surgery schedule. An initial screen will be conducted by the research staff member via telephone or in person for history of PONV, CINV, or motion sickness. Completion screening and consent will then take place prior to surgery, and will again be conducted by the research staff. Data collection will be completed by the participant either electronically or using paper and pencil. The electronic data collection will be done via File Maker Pro which is a HIPPA and MD Anderson approved system.

Randomization

Prior to surgery and after baseline data collection, all participants will be randomized into treatment or control groups using a form of adaptive randomization called minimization[42] for a better group balance based on participant characteristics that might be related to outcome. The factors used in the minimization will include smoking status (never smoker, former smoker, current smoker), history of PONV, prior PONV (Yes/No/Unknown), history of CINV (Yes/No/Unknown), history of motion sickness (Yes/No), and anticipated duration of surgery (running median)). We will use a deterministic probability of 0.99 in the minimization algorithm given the small sample sizes. Randomization will be completed through FileMaker Pro database. Patients and PONV evaluators will be blinded to group assignments. The attending anesthesiologist will not be blinded to group assignment as they will perform the intervention but will not be involved in PONV assessment.

Acupoint stimulation procedure

Control group: Patients in the control group will have pads placed on at P6 and SJ5 on the contralateral arm

induction, however, electrical stimulation will not be given.

Treatment group: Patients in the treatment group will have pre-gelled silver electrodes placed at P6 and SJ5 on the contralateral arm at induction. P6 is located on the palmar aspect of the forearm 2 cun (1 cun is equivalent to the width of the interphalangeal of the thumb of the patient) proximal to the anterior crease of the wrist, between the tendons of the palmaris longus and flexor carpi radialis muscles. SJ5 is located on the dorsal aspect of the forearm directly opposite P6, 2 cun above the posterior crease of the wrist. This second electrode acts as a skin surface electrode to allow electrical current through the P6 acupoint.

After induction, and before incision, electrical stimulation will be initiated at 1mHz, 1 pulse/second using two leads on a nerve stimulator (Neurotech, LLC, Elmgrove, WI). Stimulation will be continued throughout the surgery and discontinued at the time of extubation. Any residual gel from the electrodes will be removed.

Anesthetic management

After obtaining informed consent, and establishment of IV access, patients will receive premedications in the holding area, consisting of Pepcid 20mg IV, Versed 1-2mg IV, and Fentanyl 25-50mcgm IV. In the OR, standard ASA monitors will be placed and the patient will be pre-oxygenated. Induction via Propofol IV 1-2.5 mg/kg is followed by laryngeal mask placement. If endotracheal tube placement is indicated, neuromuscular blocking agent will be given IV, either Rocuronium 0.3-1.2 mg/kg or Succinylcholine 0.5-1.5 mg/kg. Anesthesia maintenance will be with inhalational agent of Sevoflurane or Desflurane. IV Fentanyl or Dilaudid will be titrated in accordance with the patient's individual physiological response to the surgical stimulation. Decadron 10 mg IV x1 will be given intraoperatively and Zofran 4 mg IV x1 and Phenergan 6.25 mg IV x 1 will be given at closing. The airway will be extubated in accordance with standard guidelines of care, and the patient will be brought to the PACU.

Antiemetics

All patients will receive standard prophylactic antiemetics consisting of Zofran 4 mg IV x1, Dexamethasone 10 mg IV x 1, Phenergan 6.25 mg IV x 1, and Pepcid 10mg x 1 intraoperatively as noted above. Rescue treatment for PONV will be according to our standard post-operative algorithm, i.e. for PONV occurring less than 4 hours following PACU arrival: Granisetron 1 mg IV x 1. If ineffective, this can be followed by Promethazine 6.25 mg IV up to 2 doses, after which the PACU attending is called for further intervention. For PONV occurring greater than 4 hours following PACU arrival, Ondansetron 4 mg IV can be given for two doses.

Assessment

Assessment of PONV and Pain will be conducted by the PACU nurse or research member. Per PACU procedures, the nurse will also determine when the patient is ready for PACU discharge. This nurse or research member will be blinded to group assignment.

Anesthesiologist training

P6 NBMN stimulation will be performed by a team of 4 MDACC anesthesiology faculty members. Each member has experience in using NBMN stimulation. Each participant will have training in P6 and SJ5 acupoint location with a licensed acupuncturist ([name]) and will be observed placing NBMN monitor on appropriate acupoints.

3.4 Pretreatment evaluation: Prior to beginning treatment, the following will be provided/obtained:

- a. Review of the nature and purpose of the study with potential subjects and verification that the patient meets all eligibility criteria.
- b. Written informed consent from patients who agree to participate in the study prior to any study procedures.

- c. Complete history and physical examination of eligible subjects.
- d. Review and documentation on the worksheet of specific medical history information including type of malignancy and previous surgical history.
- e. Documentation of all medications taken by the patient in the preceding 30 days.
- f. Review of the patient's available medical record to ensure that inclusion and exclusion criteria have been met.
- g. Smoking status as stated in electronic medical record.
- h. Acupuncture Expectancy Scale (AES). This 4-item instrument will be administered at time of consent.

3.5 Measurement of effects:

- 1. PONV: Nausea and vomiting will be assessed at baseline (regain of consciousness as defined by ability to answer questions regarding presence or absence of nausea and pain), every 15 minutes until discharged from PACU. Nausea will be assessed verbally on an eleven-point scale (0=no nausea to 10=worst nausea imaginable). Vomiting is defined as the forceful expulsion of gastric contents from the mouth. Retching, i.e. an active attempt to vomit without expulsion of gastric contents, will be categorized as vomiting. Complete control will be defined as no nausea ≥ 3 , vomiting, or use of anti-emetics during PACU stay. Incidence of nausea, intensity of nausea, incidence of vomiting, and number of vomiting episodes will also be measured.
- 2. Feasibility as defined by at least 20% of screened patients meeting inclusion criteria ability, 50% of these patients consenting, and 75% of patients within the acupuncture study arm completing all procedures.
- 3. Use of rescue anti-emetics. Use of rescue antiemetics will be as per PACU protocol and will be abstracted from the electronic medical record.
- 4. Patient satisfaction. Patients will be asked to rate their satisfaction with PONV management at time of discharge from PACU (0= very dissatisfied to 10= most satisfied imaginable).
- 5. Pain. Pain will be assessed every 15 minutes verbally on an eleven-point scale (0=no pain to 10=worst pain imaginable).
- 6. Postoperative analgesic use. Total MEDD of postoperative analgesia will be abstracted from the electronic medical record.
- 7. Total time in PACU will be calculated from medical record.
- 8. Need and basis for hospital admission will be abstracted from the medical record.
- 9. A maximum of 10 cubic centimeters of whole blood will be collected intra-operatively in an anti-coagulant treated tube and stored at -80°C until ready for processing to explore the associations between genetic polymorphisms in COMT, 5HT3, OPRM1, and DRD2 and response to P6 stimulation.

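### Allocation is fixed before surgery although the arms are not described as differing until after induction, so small, avoidable losses can fall after randomization

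*Combined protocol and SAP*

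**What the plan says.** On timing, the Randomization paragraph of section 3.3 reads: "Prior to surgery and after baseline data collection, all participants will be randomized into treatment or control groups". That gives an order and a latest time, but not how long before surgery the allocation is made.

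The Acupoint stimulation procedure in the same section describes what each arm receives:

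- Treatment: "Patients in the treatment group will have pre-gelled silver electrodes placed at P6 and SJ5 on the contralateral arm at induction". Then: "After induction, and before incision, electrical stimulation will be initiated".
- Control: "Patients in the control group will have pads placed on at P6 and SJ5 on the contralateral arm"; "however, electrical stimulation will not be given".

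On losses, section 3.2 expects no attrition in general but adds that "we still may have a few drop-outs between randomization and intervention". Its accrual forecast rests on "conservative estimates of 70% acceptance and including a 5% drop-out rate".

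Section 3.8 sets 88 per arm. It bases the primary analysis on observed data, and adds sensitivity analyses only if missing data or drop-outs exceed 10% in either arm. It names no analysis set and gives no rule for a patient who is randomized but never reaches the intervention.

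**The concern.** A patient who is randomized and then lost before the arms diverge contributes nothing to the comparison but has to be accounted for in it. The only loss the plan foresees lies in this interval, and nothing in the text requires the allocation to be known that early. Consent, baseline data and all the minimization factors are available before surgery, so they can be entered then and the allocation drawn later.

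Three things are at stake, all modest:

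- some precision, if lost patients are not replaced;
- a loss of randomized patients that the plan would not examine further, because 5% is below its own trigger;
- the anesthesiologist, who is not blinded, may know the arm while choosing within the ranges that section 3.3 allows for premedication and induction. The plan itself names perioperative narcotics as a risk factor for the outcome.

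**Working it through.** **Inputs.** From section 3.8: PONV 0.40 (control) and 0.25 (experimental), one-sided alpha 0.10, power 80%, 88 per arm. From section 3.2: about 350 eligible patients a year, 70% acceptance, 5% drop-out, 176 patients in 10 months.

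**1. Reproduce the 88.** With the pooled variance under the null, no continuity correction, and mean rate 0.325:

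n = [1.2816 × √(2 × 0.325 × 0.675) + 0.8416 × √(0.40 × 0.60 + 0.25 × 0.75)]² / 0.15²
= [1.2816 × 0.6624 + 0.8416 × 0.6538]² / 0.0225 = 87.006, rounded up to 88.

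The plan's figure is confirmed.

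**2. Power by number analysed.** Power = Φ{[0.15 × √n − 1.2816 × 0.6624] / 0.6538}.

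| Analysed per arm | Power |
|---|---|
| 88 (no loss) | 80.3% |
| 84 | 78.9% |
| 83.6 (5% loss) | 78.8% |

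A 5% loss is 0.05 × 176 = 8.8, or about 9 patients, leaving 0.95 × 88 = 83.6 per arm. The fall is 80.3 − 78.8 = 1.5 percentage points.

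**3. Is 176 before or after drop-outs?** The two sections can be read differently.

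- Section 3.2: 350 × 0.70 × 0.95 = 232.75 patients a year net of drop-outs, which is 194 in 10 months. Since 194 exceeds 176, the 176 can be read as net, and then no power is lost.
- Section 3.8: 1,760 × 0.20 × 0.50 = 176 consenting = 2 × 88. On that reading there is no allowance for loss after consent.

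A loss of 0 to 1.5 points covers both readings. It also covers the unknown lead time: if allocation already takes place in the holding area, little of the 5% may fall after it.

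**4. The 10% trigger.** Spread evenly, 5% is about 4.4 patients per arm, well below the threshold of 8.8. Nine losses would reach it only if all nine fell in one arm (9/88 = 10.2%).

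**5. When do the arms first differ?** Set side by side, the two procedure descriptions name the same points on the same arm and differ only in whether current is applied. One reservation applies: the control text says pads and the treatment text says pre-gelled silver electrodes. If these are different items, the arms diverge at placement, around induction, and not at the start of stimulation. That is still later than the text requires the allocation to be made.

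**The case against.** The strongest reply is that the effect is small and partly hypothetical. The plan gives no lead time and no causes for the drop-outs, the 5% is a cautious accrual allowance, and section 3.2 can be read as delivering 176 after drop-outs. All of this stands, and it is why the size is given as a range starting at zero.

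A reader might go further in three ways that the documents do not support.

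- *That power must fall below 80%.* It does so only if lost patients are neither replaced nor already allowed for, and the text is ambiguous on this.
- *That lost patients stay in the analysis unstimulated, at the control rate, and dilute the effect.* A patient whose operation is cancelled has no PACU outcome. A patient switched to a paravertebral block is expected, by section 3.2, to have less PONV. Only a withdrawal that still allowed assessment would fit.
- *That the randomized comparison is broken.* Patients are blinded and the written care before induction is the same in both arms, so losses at that stage have no shown link to allocation. The demonstrated cost is precision.

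It is also fair to say that late release protects little of the anesthesiologist's discretion. No section says when the anesthesiologist learns the arm, and opioid titration during surgery remains unblinded whatever is done. Only premedication and induction choices would be shielded.

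**Conclusion.** The point holds as a cheap improvement in design; it does not show a flaw that threatens the result. The plan allocates earlier than its own procedures need, and it locates its only foreseen loss in the resulting gap. At most about 9 of 176 randomized patients and 1.5 points of power (80.3% to 78.8%) are at issue; at least, nothing.

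The upper figure assumes that the full 5% is lost after randomization, evenly by arm, is left out of the observed-data analysis and is not replaced. The benefit for the conduct of anesthesia is real but limited to the period before stimulation, and assumes that the anesthesiologist would otherwise learn the arm before then.

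**What to change.** Amend the Randomization paragraph of section 3.3 as follows.

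- Complete consent, baseline data and the minimization factors before surgery.
- Run the FileMaker minimization and release the allocation to the anesthesiologist as late as practicable, ideally after induction and pad placement and just before stimulation would start. If the control pads differ from the treatment electrodes, release it at induction.
- Count patients lost before that moment as consented but not randomized, and report their number and reasons in the feasibility results, so that the completion rate in the stimulation arm is not flattered by their absence.
- Continue accrual until 88 per arm are randomized.

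The cost is protocol wording and releasing the allocation in the operating room between induction and incision. The team should confirm that this is workable, including whether assignment of the four trained anesthesiologists depends on the arm.

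If late release proves impractical, the alternative is to keep early allocation, state its timing, give a rule for patients randomized but not treated, and randomize 88 / 0.95 = 92.6, so 93 per arm (186 in total), to analyse 88.
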